3.1 General Design

We propose to conduct an open-label pilot study to preliminarily assess the efficacy and safety of oral curcumin in adult patients with PSC. Fifteen patients with PSC will receive one 750 mg CuraMed® softgel (EuroPharma, Inc.) by mouth twice a day for 12 weeks. Of note, each 750 mg CuraMed® softgel supplies 500 mg of highly bioavailable BCM-95 curcumin. A positive study, based on significant improvement in serum liver biochemistries, will establish the basis for further evaluation of curcumin in a larger, longer-term clinical trial.

Table 1 in section 6 summarizes the patient evaluation and study procedures. Briefly, prior to study entry, a complete history will be obtained and physical examination performed. Serum Alkaline Phosphatase, AST, total bilirubin, albumin, C-reactive protein, complete blood count, and creatinine will be measured. A blood pregnancy test will be performed on female patients of child bearing potential. Standardized questionnaires regarding health status (SF-36 Health Survey and Chronic Liver Disease Questionnaires), fatigue (Fisk Fatigue Impact Scale) and pruritus (5-D Pruritus scale) will be completed by participants at baseline and at 12 weeks. Phone calls will be made to participants weekly during the study, at completion of the study (i.e. at 12 weeks of therapy) and/or early termination, and at two weeks after completion of the study to monitor for any adverse events or effects of the study drug. Study staff will specifically inquire about local and systemic adverse effects including gastrointestinal upset, nausea, diarrhea, signs of anemia (e.g., weakness, fatigue), and rash; during weekly phone or in person

interviews. Participants will be instructed to contact study nurse coordinators with the development of any possible symptoms related to therapy.

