1.4 Clinical Data to Date

Curcumin has demonstrated high tolerability, safety, and efficacy in multiple studies including randomized controlled trials involving healthy individuals as well as patients with a variety of hepatic and non-hepatic inflammatory, degenerative, malignant, neuropsychiatric, and other illnesses.^{11-15, 29-35} Collectively, these studies have demonstrated anti-inflammatory, hepatoprotective, anti-fibrotic, immunomodulatory, and anti-carcinogenic activities of curcumin. No significant toxicity has been reported following either acute or chronic administration of turmeric extracts at standard doses. In a minority of patients, mild side-effects as nausea, diarrhea, headache, somnolence, and contact dermatitis (with topical use) have been reported.^{11-15, 29, 30}

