1.5 Dose Rationale and Risk/Benefits

In this pilot study, patients will receive 1500 mg of highly bioavailable BCM-95 curcumin®, which is supplied in one 750 mg CuraMed® softgel (EuroPharma, Inc.), to be taken orally twice a day for 12 weeks. Each softgel contains 500 mg of pure, highly bioavailable curcuminoids. This dose and route is based on recent published clinical trials, wherein curcumin has been found to be well-tolerated, safe, and efficacious in inflammatory and other disorders.^{12, 31-33, 35} Although previous studies have studied twice and three times a day regimens, we have chosen to

pursue the former given convenience and ease of adherence for patients and lack of inferiority data with this dosing regimen.

As described above, serious adverse effects have not been reported with even high doses (e.g. 10x higher than those used herein) of curcumin.^{14, 29} Mild adverse effects have been reported, however these have been uncommon and resolved with curcumin dose reduction or discontinuation.^{11-15, 29, 30, 36} These effects have included: yellow stool, diarrhea, headache, rash, increase in ALK or lactate dehydrogenase.)

2 Study Objectives

Primary Objective: to determine the change in serum Alkaline Phosphatase following 12 weeks of curcumin treatment as a biomarker of therapeutic efficacy.

Secondary Objective: to determine: 1) change in serum AST, total bilirubin, albumin, C-reactive protein, and Mayo PSC risk score following 12 weeks of curcumin treatment compared to baseline values as markers of biochemical improvement; 2) change in self-reported health status, fatigue severity, and pruritus (as assessed by standardized questionnaires) following 12 weeks of treatment compared to baseline values as markers of symptomatic improvement, and 3) the adverse events occurring during 12 weeks of curcumin treatment in patients with PSC.

3 Study Design

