3.4 Primary Safety Endpoints

We will monitor for adverse events occurring during 12 weeks of curcumin treatment as part of this study. In addition, occurrence of any of the following will be considered a treatment failure:

- Deterioration of liver biochemistries (doubling of bilirubin and/or increase in AST, ALT, and alkaline phosphatase levels $\geq 3x$ upper limit of normal or baseline levels without mechanical obstruction)
- Voluntary drug/study discontinuation for any reason (e.g. worsening of fatigue or pruritus or development of diarrhea, headache, nausea, or rash)
- Death
- Liver transplantation

4 Subject Selection Enrollment and Withdrawal

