8.1.1 Investigator reporting

The investigators will personally supervise the study. An adverse event is defined as any unfavorable and unintended diagnosis, symptom, or disease temporarily associated with use of the study medication, whether or not related to the medication. Worsening of the pre-existing clinical condition will be considered an adverse event and, possibly, treatment failure.

The investigators will use the following definitions to assess the relationship of the adverse event to the use of study drug:

1. Probably related: Adverse event has a strong temporal relationship to study drug or recurs on re-challenge and another etiology is unlikely or significantly less likely.
2. Possibly related: Adverse event has a strong temporal relationship to the study drug and an alternative etiology is equally or less likely compared to the potential relationship to study drug.
3. Probably not related: Adverse event has little or no temporal relationship to the study drug and/or a more likely alternative etiology exists.
4. Not related: Adverse event is due to an underlying or concurrent illness or effect of another drug and is not related to the study drug (e.g., has no temporal relationship to study drug or has a much more likely alternative etiology).

Adverse events will be classified according to severity into: mild (transient and easily tolerated by the participant), moderate (causes the participant discomfort and interrupts the

participant's usual activities), or severe (causes considerable interference with the participant's usual activities and may be incapacitating or life-threatening). A serious adverse event is defined as any untoward medical occurrence that results in death, is life-threatening, requires or prolongs hospitalization, causes persistent or significant disability/incapacity, or, in the opinion of the investigators, represents other significant hazards or potentially serious harm to research participants.

The investigators will be responsible for communicating adverse events to the Mayo Institutional Review Board (IRB), the Data and Safety Monitoring Board, Co-investigators, and the Food and Drug Administration. The following information will be recorded in the study database and provided as indicated:

- Medical record number:
- Disease/histology (if applicable):
- The date the adverse event occurred:
- Description of the adverse event:
- Relationship of the adverse event to the research (drug, procedure, or intervention):

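### The symptoms asked about by name in section 3.1 leave out headache (also somnolence and yellow stool), and LDH is never measured, although the protocol itself lists these as reported curcumin effects

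*Combined protocol and SAP*

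**What the plan says.** Secondary objective 3 in section 2 is to determine "the adverse events occurring during 12 weeks of curcumin treatment in patients with PSC". Section 3.1 sets out how symptoms are collected. Phone calls are made "to monitor for any adverse events or effects of the study drug", and within them "Study staff will specifically inquire about local and systemic adverse effects including gastrointestinal upset, nausea, diarrhea, signs of anemia (e.g., weakness, fatigue), and rash". Self-report is a further route: "Participants will be instructed to contact study nurse coordinators with the development of any possible symptoms related to therapy". Section 6 adds an adverse-event assessment at weeks 3, 8, 12 and 14 that names no symptoms.

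The effects already attributed to curcumin appear in two background sections. Section 1.4 says "mild side-effects as nausea, diarrhea, headache, somnolence, and contact dermatitis (with topical use) have been reported". Section 1.5 says "These effects have included: yellow stool, diarrhea, headache, rash, increase in ALK or lactate dehydrogenase" and describes the mild effects as uncommon and as resolving when the dose was reduced or stopped. Section 3.4 counts voluntary discontinuation as treatment failure and gives as examples "worsening of fatigue or pruritus or development of diarrhea, headache, nausea, or rash".

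The laboratory tests are listed in 3.1, in the section 6 visit lists and in Table 1. None of the three includes LDH.

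**The concern.** A symptom that staff ask about by name at each contact is generally picked up more completely than one that surfaces only through a general question or because the patient raises it. The named symptoms do not match the protocol's own list of curcumin effects. Headache, the only omitted symptom that appears in 1.4, 1.5 and 3.4, is absent, while signs of anemia are included although neither 1.4 nor 1.5 reports them as an effect.

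Safety is in the study title and adverse events are a stated objective. With 15 patients and no comparator, one or two recorded cases change the profile that informs a larger trial. If nausea is recorded more often than headache, the table alone cannot show whether the drug or the questioning produced the difference. For LDH the problem is simpler: a laboratory change that is not measured cannot be reported.

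**Working it through.** The plan states no figure on this point, so there is none to reproduce. The check is a comparison of sections, followed by an illustration of scale.

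**Step 1. Effects named against effects sought.**

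| Effect | 1.4 | 1.5 | 3.4, example reason for stopping | Asked by name in 3.1 | Other planned measurement |
|---|---|---|---|---|---|
| Nausea | yes | no | yes | yes | none |
| Diarrhea | yes | yes | yes | yes | none |
| Rash | contact dermatitis, topical use | yes | yes | yes | none |
| **Headache** | yes | yes | yes | **no** | none |
| **Somnolence** | yes | no | no | **no** | none directly; fatigue is asked about and scored |
| **Yellow stool** | no | yes | no | **no** | none |
| ALK rise | no | yes | separate biochemical criterion | not applicable | entry, weeks 3 and 12 |
| **LDH rise** | no | yes | no | not applicable | **none** |
| Worse fatigue | no | no | yes | yes, as a sign of anemia | Fisk scale, entry and week 12 |
| Worse pruritus | no | no | yes | no | 5-D scale, entry and week 12 |

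Three reported symptoms are not prompted, and one reported laboratory effect is not measured. Nausea, diarrhea, rash and ALK are covered. Pruritus is not reported as a curcumin effect in 1.4 or 1.5 and has its own questionnaire, so it is not counted as a gap here.

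**Step 2. Possible scale for an unprompted symptom.** The number of patients, n = 15, comes from 4.3. The other two inputs are assumptions, because the documents give neither: p is the true proportion of patients with the symptom, and s is the share of those cases recorded when the symptom is not asked about by name.

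- Expected recorded cases = 15 × p × s
- Chance of recording at least one = 1 − (1 − p × s)^15

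| p | s = 1 | s = 0.5 | s = 0.25 |
|---|---|---|---|
| 5% | 0.75 cases; 53.7% | 0.38; 31.6% | 0.19; 17.2% |
| 10% | 1.50; 79.4% | 0.75; 53.7% | 0.38; 31.6% |
| 20% | 3.00; 96.5% | 1.50; 79.4% | 0.75; 53.7% |

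For example, with p = 10% and s = 0.5, p × s = 0.05 and 15 × 0.05 = 0.75 expected cases. The chance of at least one is 1 − 0.95^15 = 1 − 0.463 = 53.7%. Full capture would give 15 × 0.10 = 1.5 cases and 1 − 0.90^15 = 79.4%.

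At s = 0.5 the expected shortfall is 0.75 − 0.375 = 0.375 cases for p = 5%, and 3.0 − 1.5 = 1.5 cases for p = 20%. Since 1.5 calls the effects uncommon, the lower rows fit the documents better. If open questioning captures nearly everything, s is close to 1 and the shortfall disappears.

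**Step 3. LDH.** For a symptomless rise, the planned tests give s = 0. The expected recorded count is then 15 × p × 0 = 0, whatever p is. This result needs no assumed rate.

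**The case against.** A reader might infer that 3.1 sets a fixed checklist, that everything off it depends on the patient speaking up, and that the known effects of curcumin will therefore be under-counted. The documents do not support that, for four reasons.

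- The list begins with *including*, so it gives examples. The calls are meant to pick up any adverse event, section 6 repeats an open assessment, and 8.1.1 is broad: "An adverse event is defined as any unfavorable and unintended diagnosis, symptom, or disease temporarily associated with use of the study medication". A headache mentioned in answer to a general question would be recorded. The adverse-event worksheet mentioned in 8.1 is not among the documents and may contain further prompts.
- Several known effects are already asked about or measured, as the table shows. The gap is confined to a few items.
- A patient who stops because of headache is still captured, because 3.4 counts voluntary discontinuation for any reason and 3.1 provides a contact at early termination.
- LDH enters no endpoint, discontinuation criterion or stopping rule. An isolated rise without symptoms arguably falls outside a definition built on diagnosis, symptom or disease. With no control arm, a rise would also be hard to attribute to the drug.

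These arguments remove any claim of a demonstrated under-count and keep the point small. They do not remove it. The protocol chose to name some symptoms, and an open question cannot be assumed to capture the unnamed ones equally well. The self-report instruction refers to symptoms related to therapy, which asks the patient to make that link, and this is a weak route for something as ordinary as headache. No amount of open questioning will detect a symptomless laboratory change.

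**Conclusion.** The point holds as a minor one. Headache is the clearest symptom gap, because the protocol names it three times and does not prompt for it. Somnolence and yellow stool rest on one section each, and somnolence is partly approached through fatigue. For all three, the documents support only a risk of uneven ascertainment. Its size cannot be derived from them, and the shortfall of roughly 0.4 to 1.5 cases among 15 patients depends wholly on assumed rates of 5% to 20% and an assumed capture of one half.

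The LDH gap is certain as a matter of fact: a reported effect is measured at no visit. Its consequence is small, because no decision in the plan depends on LDH. Nothing here affects the primary endpoint or the sample size, and the documents give no reason to think that severe events would escape the planned contacts.

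**What to change.** In 3.1, add headache, somnolence and stool color to the symptoms that staff ask about by name, and ask the same set at every contact. Keep the open question for everything else. In section 6 and Table 1, add LDH to the blood already drawn at entry, week 3 and week 12; alternatively, state in the protocol that LDH changes will not be assessed.

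While editing, reconcile the contact schedule, since it determines how often the questions are put: 3.1 and 5.5 describe weekly calls, whereas section 6 and Table 1 show contacts at weeks 3, 8, 12 and 14.

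The cost is a short addition to the questions, one extra assay on existing draws (to be requested also where a local laboratory is used), and somewhat more mild events recorded. No extra visit is needed.

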3.2 Primary Study Endpoints

The primary study endpoint in this study will be treatment success, as determined by the proportion of PSC patients who experience clinically significant improvement in Alkaline Phosphatase, as defined by: 1) a $\geq 40\%$ reduction in serum Alkaline Phosphatase (as compared to baseline value)³⁷ or 2) a decrease in serum Alkaline Phosphatase to less than 1.5 times the upper limit of normal following 12 weeks of curcumin treatment.³⁸

Notably, serum Alkaline Phosphatase values have been repeatedly associated with disease response and prognosis,³⁹⁻⁴¹ thus this readily measured biochemical test is an important endpoint and biomarker in studies of patients with PSC.

3.3 Secondary Study Endpoints

Secondary efficacy endpoints will include change in: 1) serum AST, total bilirubin, albumin, C-reactive protein, and Mayo PSC risk score⁴² following 12 weeks of curcumin treatment compared to baseline values as markers of biochemical improvement and 2) change in self-reported health status, fatigue severity, and pruritus (as assessed by standardized questionnaires) following 12 weeks of treatment compared to baseline values as markers of symptomatic improvement.

3.4 Primary Safety Endpoints

We will monitor for adverse events occurring during 12 weeks of curcumin treatment as part of this study. In addition, occurrence of any of the following will be considered a treatment failure:

- Deterioration of liver biochemistries (doubling of bilirubin and/or increase in AST, ALT, and alkaline phosphatase levels $\geq 3x$ upper limit of normal or baseline levels without mechanical obstruction)
- Voluntary drug/study discontinuation for any reason (e.g. worsening of fatigue or pruritus or development of diarrhea, headache, nausea, or rash)
- Death
- Liver transplantation

4 Subject Selection Enrollment and Withdrawal

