4.1 Inclusion Criteria

Inclusion criteria will be as follows:

- Diagnosis of PSC established by all of the following criteria:^{27, 43}
 - ALK $>1.5x$ upper limit of normal for at least 6 months prior to study enrollment

- Cholangiography demonstrating intrahepatic and/or extrahepatic biliary dilation, beading, and/or strictures consistent with PSC
- Age 18-75 years
- Male or female sex
- Women of child-bearing potential willing to use birth control for the duration of the study
- Informed consent provided by the patient for study participation

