4.4.1 When and How to Withdraw Subjects

Participants will be withdrawn from the study if they experience a CTCAE 4.0 criteria grade 3 or higher adverse event, are unable to adhere to the study protocol, inadvertently become pregnant during the study (in which case they will be referred to their primary physician for obstetric care), or experience treatment failure as described in section 3.4 above.

Participants may voluntary withdraw from the study for any reason. Patients who withdraw from the study (or decline participation) will not be penalized in any way. Specifically, they do not have to be in this study to receive or continue to receive medical care from Mayo Clinic.

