5.9.3 Dispensing of Study Drug

A 12 week supply of the study drug will be assigned and dispensed to each study participant. Drug reconciliation checks will be performed by the study team and documented in the medical record. Subjects will be requested to mail in any unused study drug if unable to return for the 12 week visit.

Return or Destruction of Study Drug

At the completion of the study, there will be a final reconciliation of drug shipped, drug dispensed, drug returns, and drug remaining. This reconciliation will be documented in the study file. Study drug destroyed on site per Mayo Pharmacy policy.

6 Study Procedures

Study procedures are summarized in section 3.1 as well as in Table 1.

Screening Visit (-28 to Day 0)

Screening assessments will be completed within 28 days of the baseline/Day 1 visit.

The following procedures will be performed and documented:

- Obtain signed informed consent
- Determine inclusion eligibility
- Obtain medical history
- Perform complete physical examination
- Obtain body height and weight
- Obtain vital signs (resting blood pressure, pulse, respiratory rate and temperature)
- Obtain details of concomitant medications
- Obtain blood samples for
 - Alkaline phosphatase
 - AST

ALT
Total bilirubin
C-reactive protein
Complete blood count (CBC)
INR
Sodium
Creatinine
Albumin
Stored serum
Serum pregnancy test for females of childbearing potential only
Questionnaires
Health status
Pruritus
Fatigue

Subjects meeting all of the inclusion criteria and none of the exclusion criteria will return to the clinic for the Baseline/Day 1 visit.

Treatment Assessments

Baseline/Day 1 Visit

Dispense study medication
Instruct the subject on the packaging, storage and administration of the study drug
If indicated, observe the subject take the first dose of the study drug

Week 3 (+- 7 days)

Obtain blood samples for
Alkaline phosphatase
AST
Total bilirubin
C-reactive protein
Complete blood count (CBC)
Creatinine
Albumin

Phone call or visit to assess for AEs, concomitant medications, and study drug compliance. Note a local laboratory can be used for obtaining the blood samples if subject is unable to return to Mayo.

Week 8 (+- 7 days)

Phone call to assess for AEs, concomitant medications, and study drug compliance. Note a local laboratory can be used for obtaining the blood samples if subject is unable to return to Mayo.

Week 12 (+- 7 days) or Early Termination

Obtain blood samples for
 Alkaline phosphatase
 AST
 ALT

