8.1 Adverse events and study discontinuation

Patients will be discontinued from the study if they: 1) request withdrawal from the study, 2) develop worsening of underlying liver function defined as doubling of serum total bilirubin and/or increase in ALK or AST to $\geq 3x$ the upper limit of normal or baseline levels without mechanical biliary obstruction, 3) have side effects to study drug (e.g. diarrhea) that are not controlled by over the counter medication (e.g. loperamide), or 4) experience an adverse event based on CTCAE 4.0 criteria of grade 3 or higher that is not related to underlying disease.

When an adverse event has been identified, the study team will take appropriated action necessary to protect the study participant and then complete the Study Adverse Event Worksheet and log. The investigators will evaluate the event and determine the necessary follow-up and reporting required (see next section).

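### ALT is part of the treatment-failure rule in 3.4 but is not scheduled at week 3, and the parallel rule in 8.1 leaves it out

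*Combined protocol and SAP*

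**What the plan says.** Section 3.4 counts as treatment failure a deterioration in liver tests, described as "doubling of bilirubin and/or increase in AST, ALT, and alkaline phosphatase levels" of at least three times the "upper limit of normal or baseline levels without mechanical obstruction". Section 4.4.1 closes its list of withdrawal reasons with "or experience treatment failure as described in section 3.4 above", so the ALT part of 3.4 belongs to a withdrawal rule.

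Section 8.1 sets out a discontinuation rule of the same kind: "doubling of serum total bilirubin and/or increase in ALK or AST to" at least three times the "upper limit of normal or baseline levels without mechanical biliary obstruction". ALT is not named there, and the enzymes are joined by *or*, where 3.4 joins them by *and*.

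Section 6 lists ALT at screening and at the visit headed "Week 12 (+- 7 days) or Early Termination". The week-3 list contains ALK, AST and bilirubin with some other tests, but not ALT. Table 1 agrees: ALT is marked at entry and 12 weeks only. Week 8 is a phone call. Its entry carries the sentence "Note a local laboratory can be used for obtaining the blood samples if subject is unable to return to Mayo", but it lists no tests, and Table 1 shows no laboratory work in that column.

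**The concern.** A withdrawal criterion needs data at a time when withdrawal can still protect the patient. For ALT, the schedule provides none before the end of treatment. Under one reading of 3.4, a patient could meet the failure rule at week 3 and stay on drug because nobody was asked to measure the enzyme concerned. A rise that resolved before the final visit would also be missing from the failure count. In addition, an investigator who follows 3.4 and one who follows 8.1 could classify the same patient differently, because the sections differ in which enzymes count and in whether one is enough.

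**Working it through.** The plan states no figure on this point, so the check sets the rules against the schedule.

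**Step 1. Rules against schedule** (3.4, 8.1, section 6 and Table 1)

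| Test | In 3.4 | In 8.1 | Entry | Week 3 | Week 8 | Week 12 or early termination |
|---|---|---|---|---|---|---|
| Bilirubin | yes | yes | yes | yes | no | yes |
| AST | yes | yes | yes | yes | no | yes |
| ALK | yes | yes | yes | yes | no | yes |
| ALT | yes | no | yes | **no** | no | yes |

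Scheduled on-treatment values before the final visit: ALT 0; bilirubin, AST and ALK 1 each. The visit lists and Table 1 agree with each other, so the gap is not a typesetting slip in one of them.

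**Step 2. When the missing ALT value matters.** If bilirubin has doubled, both rules apply whatever ALT shows. Suppose it has not, and there is no mechanical obstruction. Each of AST, ALK and ALT is then above or below threshold, giving 2 × 2 × 2 = 8 patterns. These are logical cases, not probabilities.

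- 8.1 applies if AST or ALK is above threshold: 8 − 2 = 6 patterns.
- 3.4 read as any one enzyme applies in 8 − 1 = 7 patterns. The one extra pattern is ALT above threshold with AST and ALK both below. Only there does the absent week-3 ALT leave on drug a patient whom 3.4 would withdraw.
- 3.4 read as all three enzymes applies in 1 pattern, which 8.1 also covers. If AST or ALK is below threshold at week 3, the all-three condition already fails without ALT. If both are above, 8.1 discontinues the patient and ALT is drawn at early termination. The missing ALT never changes the decision to stop. The residual problem is that 6 − 1 = 5 patterns lead to discontinuation under 8.1 without meeting the 3.4 enzyme condition.

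**Step 3. Length of the delay on the any-enzyme reading.** Count days from first dose as day 0, with full adherence. The course is 168 softgels (5.7) / 2 per day = 84 days. The week-3 draw falls on day 21 ± 7, that is day 14 to 28. The final visit falls on day 84 ± 7, and dosing ends by day 84.

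- Nominal: 84 − 21 = 63 days (9 weeks).
- Longest: 84 − 14 = 70 days (10 weeks).
- Shortest: 77 − 28 = 49 days (7 weeks).

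This is calendar arithmetic for a patient who has such a rise. It is not an effect size.

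**Step 4. What a week-3 ALT would gain.** The longest stretch of dosing without a scheduled ALT value is now 77 to 84 days. With ALT at week 3 it becomes 49 to 70 days, the same as for AST, ALK and bilirubin. The interval from week 3 to week 12 stays unsampled for every enzyme.

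**The case against.** The best defence is that the working safety scheme already hangs together without ALT. The rule in 8.1 uses bilirubin, ALK and AST, and all three are measured at week 3. The laboratory list in 3.1 also omits ALT, and ALT appears in no objective or efficacy endpoint. On this view ALT in 3.4 is a stray word, and 3.4 taken literally, with *and*, loses almost nothing. Even on the any-enzyme reading the affected case is narrow, a persistent rise is still counted at week 12, and an unscheduled ALT could be ordered.

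Much of this stands. It limits the size of the point and makes deleting ALT from 3.4 a legitimate alternative. It does not remove the mismatch: 3.4 names ALT, 4.4.1 gives 3.4 force, and nothing requires an ALT value before the final visit. The weekly calls in 3.1 ask about symptoms and would not show a silent enzyme rise.

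Stronger readings are tempting, but the documents do not support them:

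- *Liver safety is unmonitored at week 3.* It is not; bilirubin, AST and ALK are all drawn.
- *If all three enzymes must rise, the enzyme condition cannot be assessed at all at week 3.* A negative answer is available whenever AST or ALK is below threshold, and 8.1 deals with the rest.
- *The three-fold threshold should be rewritten as three times baseline.* Both sections do leave open which reference governs. Entry requires ALK above 1.5 times the "upper limit of normal for at least 6 months prior to study enrollment", and neither 4.1 nor 4.2 sets an enzyme ceiling. But a baseline-only rule for raised enzymes would put the ALK trigger above 3 × 1.5 = 4.5 times the upper limit of normal in every eligible patient. That loosens a safety rule. It is a separate question for the sponsor.

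**Conclusion.** The point holds and is minor. The mismatch between 3.4, 8.1 and the schedule is certain from the text. Its clinical consequence is conditional. It arises only if any one enzyme suffices under 3.4, and only for a patient whose ALT alone is above threshold at week 3. For that patient, detection is delayed by nominally 63 days of dosing (49 to 70), assuming full adherence and no unscheduled test. The event is lost from the failure count only if it resolves before the final visit. The documents give no frequency for isolated ALT rises, so no expected number of missed failures is offered. If all three enzymes must rise, the point reduces to inconsistent wording.

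A reader might infer that the trial's main results are affected. They are not. The primary endpoint in 3.2 uses ALK only, the stopping rule in 8.2 is written in CTCAE grades rather than the 3.4 rule, and section 7 specifies no dedicated analysis of the failure count.

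**What to change.** Add ALT to the week-3 list in section 6 and to the week-3 column of Table 1, run on the sample already drawn. Use one analyte list in 3.4 and 8.1: doubling of total bilirubin and/or a rise in any of AST, ALT or ALK, with the existing threshold and obstruction wording left as it is.

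The cost is one extra assay per patient (15 at the planned enrolment), one table cell, one line in the visit list and a shared sentence. No extra visit or needle stick is needed. The downside is possibly an occasional extra discontinuation on ALT.

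If the sponsor does not want ALT to drive withdrawal, delete it from 3.4 and align that section with 8.1, including *or* between the enzymes. This removes the inconsistency at no cost but leaves ALT unseen at week 3. Under either option, the sponsor should settle separately which reference governs the three-fold threshold when a patient enters with raised enzymes.
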